2.0 STUDY DESIGN

Primary Hypothesis:

Due to its different but relevant mechanism of action, guanfacine will be an effective adjunct to lidocaine in trigeminal nerve block for the treatment of painful trigeminal neuropathy by enhancing and prolonging pain relief compared to lidocaine alone.

Endpoints

The following endpoints will be measured to evaluate the exploratory objectives of the study assessing guanfacine and lidocaine in combination compared to lidocaine alone, in pain management in the painful trigeminal neuropathy patient.

- Primary endpoint: time to return to baseline pain (VAS) measurement after treatment with guanfacine as adjuvant to 1% lidocaine compared to 1% lidocaine alone
- Safety endpoint: comparable side effect profile of combination product compared to lidocaine alone on relevant adverse event measures: sedation, local site reaction, confusion
- Secondary endpoint: pain intensity after treatment to be measured throughout the follow-up periods on a visual analog scale (VAS)
- Secondary endpoint: quality of life after treatment to be measured using PROMIS Global Health -10 SF during the follow-up periods
- Secondary endpoint: frequency of acute trigeminal nerve pain attacks during the follow-up periods
- Secondary endpoint: total amount of rescue medications (opioid and non-opioid analgesics) for pain management during the follow-up periods
- Secondary endpoint: time to first rescue medication during the follow-up periods

Experimental Design

The trial is designed as a single-center, randomized, double-blind, controlle, 2x2 crossover pilot study with two arms: study drug (guanfacine and lidocaine combination) and active control (lidocaine alone). The target sample size is 30 study drug vs. 30 active control.

Not all participants that are randomized and initiate the first arm of the trial will *necessarily* complete *both* arms of the crossover trial. Based on previous experience, initiating the first arm of the cross over trial in 40 participants should be sufficient reach the full sample size (30 study drug vs. 30 active control). The trial will be complete and enrollment will cease upon reaching the full proposed sample size (30 study drug vs. 30 active control).

Approximately 80 patients meeting preliminary enrollment criteria will be consented for screening with the goal of roughly half being eligible to randomize and begin participation in the trial.

Inclusion Criteria

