Participants will be asked to record their pain intensity, 24- hour VAS and current VAS, before the procedure to establish a baseline pain score. Other data will be collected for secondary measures: frequency of pain attacks, basal and breakthrough opioid and non-opioid analgesic frequency and dose. Overall quality of life (PROMIS Global-10 short form) will be assessed.³⁹ Women of childbearing potential will undergo a urine pregnancy test prior to receiving the nerve block.

First trigeminal nerve block procedure: Participant will receive either study drug (guanfacine and lidocaine combination) or active control (lidocaine alone) for the trigeminal nerve block based on randomization. Participants will be monitored for pain intensity at 30-minute time intervals for the first 8 hours after block in addition to safety monitoring procedures. Participant responses will be collected at 30 minute intervals for the first 8 hours while in the recovery (first 60 minutes) and after discharge home, with responses allowed all the way until the next time point and actual time of the response being used in analysis. Assessments will be recorded according to the patient's preference, either on paper or via text message) using the Twilio application linked to REDCap. Patients will also receive a sheet with contact information for the study nurse.

First follow-up period (Day 2 to Day 14)

Participants will be monitored once daily at approximately the same timepoint for 14 days using text message generated using the Twilio application or recorded on a paper diary. Participants will also be monitored for any use of rescue medication (analgesics) once daily. The study nurse will monitor participants once weekly for overall quality of life via phone call using the PROMIS global 10 SF. Participants will be instructed to contact the study nurse with any adverse events directly by phone.

At the end of the first follow-up period, participants will be contacted for crossover to the other arm to receive the second trigeminal nerve block using the alternative drug (study drug or active control), not received during the first nerve block. At the second study visit, participants will record 24-hour VAS and current VAS, and the PROMIS Global-10 Short Form to establish baseline measurement again. Women of childbearing potential will undergo a urine pregnancy test prior to receiving the nerve block.

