If VAS < 5 on the pain scale, participants will not be eligible for second trigeminal nerve block during the visit. Study nurse will continue monitoring the participant's pain intensity (daily through day 15, and weekly thereafter) to see if the participant pain is above 5 on the pain scale and eligible for the second block. In general, the study intends that participants would receive both treatments unless they experience intolerable toxicity. If a participant is unable or ineligible to receive second trigeminal nerve block, then the participant's data collected during the first nerve block will be included in the analysis. In addition, a replacement participant will be enrolled so that the minimum number of 30 for each arm is reached. An intention-to-treat analysis will be done post-hoc to evaluate any differential progress to second block between the initial randomized groups.

Second trigeminal nerve block procedure: Participant will receive second trigeminal nerve block followed by monitoring for pain intensity at 30-minute time intervals for the first 8 hours after block, again allowing responses all the way until the next time point.

Second follow-up period (14 days)

Participants will be monitored once daily at the same timepoint for 14 days using text message generated using the Twilio application or recorded on a paper diary. Participants will also be monitored for any use of rescue medication (analgesics) once daily. The study nurse will monitor participants once weekly for overall quality of life via phone call. Participants will be instructed to contact the study nurse with any adverse events directly by phone.

[figure not shown]

Figure: 1. Study Schema

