The trigeminal block procedure is standard of care in the pain clinic. Expected effects of successful block include transient numbness, transient facial weakness including ipsilateral eyelid lag, and rare visual changes all of which resolve with the resolution of the effects of lidocaine over the typical course of 2 hours. Rare risks of the block procedure include infection, bleeding, nerve injury from the mechanical placement of the block needle. Rare risks of using lidocaine during the block procedure include intravascular or subdural injection resulting in transient unresponsiveness and/or seizure, mild sedation, bradycardia, and arrhythmias. These rare risks and side-effects must be differentiated from potential side-effects due to the addition of guanfacine. As all eligible patients are in

clinic for diagnostic nerve block as standard of care, they will receive clinical consent to treatment for the injection procedure itself and necessary x-ray radiation as part of routine care.

Common side-effects of daily oral use of guanfacine include dizziness, drowsiness, tiredness, low blood pressure, and slow heart rate. These side-effects are similar among other medications in the same class including clonidine, dexmedetomidine, tizanidine. Clonidine is also used as an intrathecal analgesic and as a perineural adjunctive injectate for regional blocks. We would expect that the side-effects of guanfacine as an adjunct to lidocaine block might additionally include increased dizziness, drowsiness, tiredness, low blood pressure, and slow heart rate. If the level of sedation experienced by at least 20% of patients in either group is greater than anticipated either by severity or duration, study enrollment will be stopped and the safety monitor engaged for an interim review of data comparing the study groups. If oversedation is occurring in only one group, an adjustment will be made to maintain monitoring for more than an hour (as is standard) until complete recovery.

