9.0 STATISTICAL CONSIDERATIONS

The effects of guanfacine adjuvant (intervention) versus active control on the time to return to baseline pain (primary) will be assessed using linear mixed-effects regression, adjusting for randomization order group and its interaction with the intervention/control indicator. A random intercept indexed by study participant will be used to account for within-participant correlation of the pre- and post-crossover measurements. The linear model assumptions will be assessed by examining residuals, conditional on the empirical Bayes estimates of random effects. If there is evidence that the linear model assumptions are violated (e.g., non-normal residuals or the very unlikely possibility of right censoring), alternative model formulations will be considered as necessary. The overall effect of intervention on the primary outcome will be tested using a two degree-of-freedom chunk test against the null hypothesis of no intervention main effect and no order-by-intervention interaction. The effects of intervention on the mean time to return to baseline will be summarized using estimates and 95% confidence intervals, stratified by order group. The effects of guanfacine adjuvant versus active control on secondary outcomes will be assessed using similar mixed-effects regression techniques as appropriate for the type of outcome (including proportional hazards, cumulative logit, logistic, and linear regression methods), adjusting for

randomization order group and its interaction with the intervention/control indicator. A random intercept indexed by study participant will be used to account for within-participant correlation. Quantitative and/or graphical regression diagnostics will be examined, and alternative model formulations will be considered as appropriate. Intervention effects will be tested and summarized as described above. No familywise hypotheses will be tested; no adjustments will be made to control any familywise type-I error probability. The type-I error rate will be fixed at 5%. All statistical analyses will be implemented in R (www.r-project.org; latest version) and the add-on package "lme4" and other packages as necessary.

9.1 Statistical power and sample size. Evidence from the medical literature and expert opinion suggests that the mean duration of pain relief after treatment with lidocaine alone (active control group) is approximately 140

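### Section 9.0 gives the repeatedly measured VAS outcome only a participant random intercept and no reduction to one value per block; daily readings entered that way would give too small a treatment standard error

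*Combined protocol and SAP*

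**What the plan says.** For the primary outcome, time to return to baseline pain, section 9.0 fits a linear mixed model with treatment, order group and their interaction. The participant intercept is there to "account for within-participant correlation of the pre- and post-crossover measurements". Each participant has one value per block (a nerve block and its follow-up), so at most two.

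The same section then carries the approach over to all secondary outcomes, adapted to outcome type: "A random intercept indexed by study participant will be used to account for within-participant correlation". Effects are to be tested and summarised as for the primary, by the two-degree-of-freedom test of treatment and treatment-by-order at 5%. A further sentence says that diagnostics will be looked at and other formulations considered, but names neither a trigger nor an alternative.

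Section 2.0 defines the VAS secondary endpoint as "pain intensity after treatment to be measured throughout the follow-up periods on a visual analog scale (VAS"). Section 5.0 supplies the readings. On the procedure day, "Participants will be monitored for pain intensity at 30-minute time intervals for the first 8 hours after block", which is about 16 readings. In follow-up, "Participants will be monitored once daily at approximately the same timepoint for 14 days"; the first follow-up is labelled Day 2 to Day 14, which is 13 days. The footnote to the schedule table allows daily collection up to 28 days. No section gives a mean, area under the curve, time point or other reduction to one value.

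**The concern.** A participant intercept absorbs what a person's two blocks have in common. It does not absorb what is shared only by readings after the same injection, such as a good or bad fortnight, or a block that happened to be well placed. Treatment is constant within a block and changes only between blocks, so this block-specific variation is the error against which treatment must be judged. A model without a term for it estimates the error mostly from day-to-day scatter within blocks, and in effect counts 13 correlated readings as 13 independent ones.

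At stake are the p-value and confidence interval for VAS intensity, a supporting pain measure in a trial that section 9.1 describes as proof of mechanism. A VAS effect could be reported where there is none.

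**Working it through.** **The plan's own figure.** Section 9.1 states about 90% power for the primary outcome with 30 participants, a 28-minute difference and a within-subject SD of 30 minutes. SE = 30 × √(2/30) = 7.75; noncentrality = (28/7.75)² = 13.07; the two-degree-of-freedom chi-square test at 5% has power 90.9%. The stated figure is reproduced. It rests on one value per block, so the present point does not touch it.

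**Inputs for VAS.** From the documents: n = 30 completers, two blocks each, M = 13 daily readings, the two-degree-of-freedom test at 5%. Assumed, because the documents give no VAS variance or correlation: within-participant variance 1, of which a share ρ = 5%, 10% or 25% is specific to the block and the rest is independent; no drug or period effect; no trend over days 2–14.

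**Formulae.** With complete data the test depends only on within-participant contrasts.

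- True variance that governs the treatment contrast: B = Mρ + (1 − ρ).
- Residual variance that the stated model estimates: S = [(n − 2)B + 2n(M − 1)(1 − ρ)] / [n(2M − 1) − 2]. For M = 13 this is [28B + 720(1 − ρ)] / 748.
- True SE / reported SE = √(B/S).
- Rejection rate of the nominal 5% test with 2 df = 0.05^(S/B).

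| Block share ρ | B | S | SE ratio | Rejection rate |
|---|---|---|---|---|
| 5% | 1.60 | 0.974 | 1.28 | 16% |
| 10% | 2.20 | 0.949 | 1.52 | 27% |
| 25% | 4.00 | 0.872 | 2.14 | 52% |

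At ρ = 0, B = S and the test holds at 5%. With 14 readings the 5% and 10% rows become 17% and 29%. Simulated trials agree. Serial day-to-day correlation of 0.3 or 0.5, with no block share, gives about 20% or 34% in simulation with 13 readings.

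**Participants with one block only.** Section 5.0 says that such a "participant's data collected during the first nerve block will be included in the analysis", and section 2.0 expects that "initiating the first arm of the cross over trial in 40 participants should be sufficient reach the full sample size". In simulation, 30 completers plus 10 first-block-only participants give 17%, 27% and 52%. With 20 completers plus 20 first-block-only participants, which is exactly 30 blocks per arm, the rates are 16%, 27% and 53%. Keeping these participants changes little.

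**Adding the half-hourly readings without a time term.** Now M = 16 + 13 = 29. Pain falls and returns within the 8 hours. If that time course has variance V, its sum of squares, 2nMV, goes into the residual: S = [28B + 1,680(1 − ρ) + 1,740V] / 1,708.

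| V relative to within-participant variance | ρ = 5% | ρ = 10% | ρ = 25% |
|---|---|---|---|
| 1 | 8% | 21% | 49% |
| 2 | 2% | 10% | 34% |
| 3 | 0.7% | 4% | 23% |

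Simulation agrees to within about 1.5 percentage points. For scale, take an assumed 5-point fall that lasts the 140 minutes in section 9.1, which covers 4 of 29 readings: V = 25 × (4/29) × (25/29) = 2.97. For an assumed within-participant SD of 2 points (variance 4) this is 0.7 times the within-participant variance, and for an SD of 1 point it is 3 times. So both too many and too few rejections are possible.

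**Weekly outcomes.** For two weekly scores per block, M = 2 and S = [28B + 60(1 − ρ)] / 88. The rates are 6%, 7% and 11% (7%, 8% and 11% in simulation).

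**The case against.** The strongest reply is that nobody has committed to entering every reading. Secondary outcomes are to be handled like the primary, which has one value per block, and the absence of any time term fits that reading. This stands: a reader might infer that the planned VAS analysis is wrong as it is, and the documents do not establish that. They leave open whether the rule meets one value or many. But no summary is defined anywhere, while a rule on correlation is stated and the endpoint is described as repeated readings, so the risk comes from the text.

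Second, the section provides for diagnostics and other formulations. A large unmodelled time course would probably show in a residual plot. A modest block effect with flat pain is much less visible, and that is the case which inflates the error rate. With no named trigger or alternative, the repair would be chosen after seeing the data.

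Third, one might infer that the daily analysis could equally be too conservative. That would need a large trend across days 2–14. The plan points the other way: about 140 minutes of relief on lidocaine, and, in the Safety Stopping Criteria of section 7.0, effects of the block that "resolve with the resolution of the effects of lidocaine over the typical course of 2 hours". Error in either direction is supported only when the half-hourly readings are pooled in.

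Fourth, VAS is one of five secondary endpoints in a pilot, with no familywise testing and no decision rule attached to it. That limits the consequence.

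**Conclusion.** The point holds conditionally. If daily VAS readings enter the section 9.0 model as written, the treatment standard error is too small whenever readings after the same block correlate positively beyond the participant effect, as pain scores on successive days plausibly do. The size is a rejection rate of about 16%, 27% or 52% instead of 5%, at block shares that are assumptions and not figures from the documents. If the half-hourly readings are pooled in without a time term, the direction cannot be known in advance. If VAS is reduced to one value per block, the problem does not arise.

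It does not extend to the primary analysis, its stated power, or the outcomes with one value per block (total rescue medication, time to first rescue). For weekly PROMIS scores and attack counts the effect is small, about 6% to 11%. This should be settled before analysis, but it is not a flaw in the trial's main comparison.

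**What to change.** State one of two rules for VAS in section 9.0.

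1. Analyse one pre-specified summary per block over a fixed window in the existing two-values-per-participant model. Keep 0–8 hours (for example mean or area under the curve) separate from days 2–14 (for example mean daily VAS).
2. Model all readings in the window, with assessment time as a fixed effect and a participant-by-period random intercept added to the participant intercept. Add serial residual correlation if needed.

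Under either rule, exclude readings after day 14. The schedule table allows daily readings up to 28 days. Sections 5.0 and 9.1 continue monitoring participants whose pain stays low, weekly after day 15 in one and daily on days 15–28 in the other. Those extra readings therefore depend on the outcome.

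Use small-sample degrees of freedom. In simulation, rule 1 rejects 6.7–7.6% of the time with a chi-square reference and 4.9–5.1% with an F reference on 2 and (completers − 2) degrees of freedom. Rule 2, with flat pain, gives 6.3–7.8% and 4.2–5.1%. This chi-square shortfall is a separate small-sample matter from the missing block term.

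Applying the same rule to weekly PROMIS and attack counts is optional.

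The cost is a short paragraph and a little more analysis work, with no new data. Intervals will usually be wider. The extra random intercept can be fitted in lme4, which the plan already names; serial correlation needs one of the other packages that it allows.

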5.0 STUDY PROCEDURE

The study is a single center, randomized, double-blind, 2 x 2 crossover pilot study with two arms; study drug (guanfacine and lidocaine combination) and active control (lidocaine alone). Adult participants between 18 and 80 years of age who have been diagnosed with painful trigeminal neuropathy will be consented for the study. The study includes three visits; an initial visit for evaluation, consent, and baseline surveys followed by two procedural visits. After each procedural visit data will be collected for 14 days. Participants will be randomized in permuted pairs (to ensure balance after every second enrollment) to receive either study drug (guanfacine and lidocaine combination) or active control (lidocaine alone) for the first nerve block procedure. Following the first procedural visit and 14-day follow up period, the study team will assess inclusion and exclusion criteria and (if eligible) schedule the second procedural visit.

Assessment	Study Visit 1: Consent and screening (Day -15 to 0)	Study Visit 2: Procedure 1 (Day 1)	Follow-up period 1 (Day 2-14)	Study Visit 3: Procedure 2 (≥15 days after procedure 1)	Follow-up period 2 (14 days after procedure 2)
		Administrative P	rocedures		
Eligibility Review	X	X		X	
Informed Consent	X				
Demographics	X				
Pain History	X				
Baseline Pain	X	X	X	X	X
Medical History	X				
Concomitant Medications	X	X		X	
Surgical/ Past Treatments History	X				
Verbal Pregnancy Screen	X				
PROMIS Global 10- SF	X	X	X \$	X	X \$
Pain Interference	X	X		X	
Pain Intensity (VAS Score)	X	X #	X %	X #	X
Frequency of Attacks	X	X	X \$	X	X \$
Rescue Medications		X %	X %	X %	X
Randomization	X				
	Cl	inical Procedures/	Assessments		•
Physical Exam (general)	X	X		X	
Physical Exam (pain)	X				
Vitals (HR, RR, Temp, BP)	X	X		X	
Height/ Weight	X				
12-Lead ECG ^	X				
Continuous ECG monitoring		X		X	
Nerve Block Administration		X		X *	
Imaging MRI/ CT report +	X				
Adverse Events		X	X	X	X
		Laboratory Pro	cedures		
Urine Pregnancy Test		X		X	
Urine Drug Screen	X				

^{#:} Collected every 30 minutes for 8 hours by text message (REDCap) or patient diary

^{%:} Collected daily for up to 28 days by text message (REDCap) or patient diary

Collected weekly for up to 4 weeks by study nurse phone call

If pain score >5

^{+:} Review recent imagining, if not available then order as standard of care
^: Order 12-lead ECG as standard of care if one not available within 2 months of screening visit

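### The primary 2-df test pools the drug effect with the period effect, so a difference between first and second block alone can make the guanfacine test significant

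*Combined protocol and SAP*

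**What the plan says.** Section 5.0 describes the design: "The study is a single center, randomized, double-blind, 2 x 2 crossover pilot study with two arms", with participants allocated 1:1 to the two orders in permuted pairs.

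Section 9.0 analyses the primary endpoint with a linear mixed model for treatment, "adjusting for randomization order group and its interaction with the intervention/control indicator", and a random intercept per participant. No period term is listed. The effect of guanfacine is then to be "tested using a two degree-of-freedom chunk test against the null hypothesis of no intervention main effect and no order-by-intervention interaction". Results are to be "summarized using estimates and 95% confidence intervals, stratified by order group". On error control the section says "The type-I error rate will be fixed at 5" per cent. Secondary outcomes are to be tested and summarized in the same way.

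No section names a 1-df, period-adjusted treatment test or a single treatment difference. No section says how to read a significant joint test when the two order groups disagree.

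**The concern.** In a 2x2 crossover there are four cells: two orders by two periods. Once treatment and order are in the model, the remaining degree of freedom between cells is the period contrast, and the order-by-treatment interaction is that same contrast under another name. Testing treatment and interaction jointly therefore tests drug and period together, while the plan reads a rejection as an effect of the intervention.

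The period effect need not be zero. Section 2.0 admits only participants with no earlier trigeminal nerve block for pain, so the first study block is their first such block and the second is not. If the two blocks differ in duration for any reason unrelated to guanfacine, the primary test can be significant with an inert adjuvant. The stated 5% error rate then does not apply to the guanfacine question. Section 9.1 says a successful result would lead to further formulation work, so a false positive has consequences even in a pilot.

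The reporting plan has the same fault. Each order-specific estimate mixes drug and period effects, and each rests on half the participants.

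**Working it through.** **Inputs.** From Sections 9.0 and 9.1: alpha 0.05; control mean 140 minutes; target difference 28 minutes (20%); between- and within-subject SD 30 minutes each; n = 30 completers; stated power about 90%. The documents give no period effect. I assume a constant one, p = second minus first block, from 0 to 35 minutes, with no carryover.

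**Aliasing.** Let t be the drug effect. The expected guanfacine-minus-lidocaine difference is:

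- guanfacine first: t − p
- lidocaine first: t + p

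The average of the two is t, and half their difference is p. The interaction is thus the period effect, up to scale. For example, with t = 0 and p = 28 the planned model returns a treatment coefficient of −28 and an interaction of +56. That is −28 minutes in one order group and +28 in the other.

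**Noncentrality of the joint test.** A within-participant difference has SD 30√2 = 42.4 minutes. With n/2 per order,

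ncp = (n/2)·[(t − p)² + (t + p)²]/(2·30²) = n(t² + p²)/1800.

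Drug and period enter symmetrically, so the test detects a period effect exactly as often as a drug effect of the same size.

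**The plan's own figure.** With t = 28, p = 0 and n = 30, ncp = 30·784/1800 = 13.07. Power on 2 df is 90.9% (chi-square) or 87.5% (F with 2 and 28 df). The stated figure of about 90% is reproduced by the 2-df chi-square test. A 1-df test would give 95.1% (z) or 93.7% (t).

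**Rejection with zero drug effect (t = 0, n = 30).**

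| p (min) | ncp | chi-square | F(2, 28) |
|---|---|---|---|
| 0 | 0 | 5.0% | 5.0% |
| 5 | 0.42 | 8.3% | 7.9% |
| 10 | 1.67 | 19.4% | 17.8% |
| 14 | 3.27 | 34.7% | 31.5% |
| 20 | 6.67 | 63.3% | 58.3% |
| 28 | 13.07 | 90.9% | 87.5% |
| 35 | 20.42 | 98.7% | 97.6% |

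A 20,000-run simulation of the paired-difference F test gave 31.4%, 58.1% and 87.6% at 14, 20 and 28 minutes. In the same runs the 1-df period-adjusted treatment test rejected between 4.9% and 5.3% of the time for p = 0, 14, 20 and 28.

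**Incomplete pairs.** Section 9.1 keeps data from participants who receive only the first block, and Section 2.0 expects about 40 to start. With 20 completers and 20 first-block-only participants (30 blocks per arm), the joint test rejects 27.2% of the time at p = 14 and 81.4% at p = 28 (chi-square, t = 0). The fault is somewhat smaller but of the same kind.

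**Precision of the planned estimates.** Each order-specific estimate has SE √(1800/15) = 10.95 minutes. The pooled effect has SE √(1800/30) = 7.75 minutes. With t = 28 and p = 14 the two planned estimates would be expected to read 14 and 42 minutes.

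**The case against.** The strongest reply is that the order-stratified estimates would expose a pure period effect, because their expected values are −p and +p. Often they would. In the simulation with t = 0 and p = 28 the joint test rejected in 87.6% of runs, and in 87.1% of all runs it rejected with opposite signs in the two groups. At p = 14 the figures were 31.4% and 28.7%. A careful reader would seldom see both order groups favour guanfacine. This softens the fault but does not remove it, because the plan does not make its conclusion depend on agreement between the groups. By symmetry, about half of the false rejections have an average favouring guanfacine: roughly 16% of trials at p = 14 and 44% at p = 28.

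Four further points deserve weight:

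- **The period effect is assumed.** This is correct. With p = 0 the test holds 5%. The blocks are at least 15 days apart, and baseline pain is re-measured and a pain threshold re-applied before the second block, which should make the two starting states more alike. The remaining argument is that the first block is the participant's first. It is plausible, but nothing in the documents quantifies it. Equally, the plan does not argue that p is zero.
- **The trial was sized for the test it names.** This also stands. Power of 87.5% to 90.9% exceeds the 80% target, so the loss against a 1-df test is an inefficiency rather than an error.
- **Order might mean period.** The joint test would then hold 5% under a pure period effect. But Section 9.0 speaks of randomization order groups and stratifies by them, which is the allocated sequence.
- **The interaction guards against carryover.** It does not do so cleanly. With carryover cG from guanfacine and cL from lidocaine, the differences are t − p − cG and t + p + cL. Their average is t − (cG − cL)/2 and their half-difference is p + (cG + cL)/2. The interaction cannot separate period from carryover, and the differential part biases the average unseen.

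**Conclusion.** The concern holds. As written, the primary test is not specific to guanfacine: it tests drug and period effects together and gives them equal weight. Its 5% error rate for the guanfacine question holds only if the period effect is zero. Otherwise, under the plan's own variance and sample size, the rate rises to 17.8% for an assumed 10-minute period effect and 87.5% for 28 minutes (F reference). These figures rest on a constant period effect, no carryover and 30 complete pairs; with incomplete pairs the inflation is lower but still large. The fault lies in the choice of test and summary. The design and the fitted model are sound, since the treatment effect averaged over the two orders is free of any constant period effect.

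**What to change.** In Section 9.0, specify fixed effects for treatment, period and randomization order group, with a random participant intercept. This is the planned model re-parameterised and gives the same fit. Then:

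- make the primary test the 1-df treatment contrast, averaged over the two orders;
- report one treatment difference with its 95% confidence interval;
- report the period effect separately, and keep the order-specific estimates as descriptive only;
- apply the same rule to the secondary outcomes.

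In Section 9.1, re-run the simulation for this test and include a layout with first-block-only participants. For 28 minutes, power with 30 completers is 93.7% (t) or 95.1% (z). With 20 completers and 20 first-block-only participants it is 88.4% (z), against 81.4% for the joint test (chi-square).

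The cost is a change of SAP wording and one re-run of the power simulation. No additional participants, visits or data are needed, and no power is lost.
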